### 15.2.3 Subject-reported Outcomes/Health-Related Quality of Life

*Analysis sets: HRQoL*

- Health-related quality of life (HRQoL) will be assessed by the EuroQOL 5-dimensions questionnaire (EQ-5D), the European Organization for Research and Treatment of Cancer (EORTC) QLQ-C30 supplemented by the gastric cancer module QLQ-STO22 questionnaire. Details on these questionnaires are provided in the following sections. The analyses specified in this section will be performed for HRQoL analysis set. CCI

The following analyses will be performed for each of these score/scale systems: HRQoL questionnaires compliance and full completion rate

HRQoL compliance rate across all instruments will be summarized by considering the EQ-5D-5L, the QLQ-C30, and the QLQ-STO22 for each scheduled visit using the following definition:

$$\%Compliance = 100 \times \frac{\text{number of subjects with at least one HRQoL questionnaire available}}{\text{number of subjects for whom a HRQoL questionnaire is expected}}$$

$$\%Full\ completion\ rate = 100 \times \frac{\text{number of subjects with all items in HRQoL questionnaire available}}{\text{number of subjects for whom HRQoL questionnaire is expected}}$$

The compliance and full completion rate for each questionnaire will be displayed using a line plot with time on the x-axis and completion rate on the y-axis. Separate lines will be presented for each treatment arm.

- HRQoL questionnaires descriptive statistics

Observed and change from Maintenance Phase baseline values will be summarized descriptively at planned visits during the treatment phase, the Discontinuation visit, End of Treatment visit, and 30-day Safety Follow-up visit by treatment arm. The percent of subjects at the worst possible score and at the best possible score (see sub-sections below, for details on best and worst scores) will be reported. In addition, the best (biggest improvement), worst (largest decline), and last observed post-Maintenance Phase baseline change from Maintenance Phase baseline values will be summarized.

Change from Maintenance Phase baseline will also be displayed using a line plot with time point (scheduled visit) on the x-axis, mean change score on the y-axis, 95% CI's around each mean score, and separate lines for each treatment arm.

If there are multiple complete assessments for any scheduled visit during the treatment phase, the assessment that is closest to the planned visit per protocol will be used in the analysis. If there are multiple complete assessments at Discontinuation visit and End of Treatment visit, the first assessment will be used in the analysis.

- Longitudinal analysis of change from Maintenance Phase baseline

A mixed-effects model repeated measures (MMRM) analysis will evaluate longitudinal change from baseline on the QLQ-C30 physical function scale and the QLQ-STO22 symptom scales. Covariates will include the Maintenance Phase baseline score for the domain score being evaluated and the randomization stratification factor. The questionnaire completion time point (Maintenance Phase-study day), including both scheduled and unscheduled visits, will be analyzed as a continuous variable. The overall significance of the difference between the MMRM trajectories for the treatment arms will be tested. An unstructured covariance structure will be used, if possible, though a simpler covariance structure will be used if the model does not converge.

- Subject level change from Maintenance Phase baseline

For the HRQoL domain scores analyzed using MMRM, an empirical cumulative distribution function (eCDF) curves, separated by treatment arm, will display the proportion of subjects who experienced specific changes from Maintenance Phase baseline to end of treatment. For each eCDF, the range of change scores will be displayed on the x-axis, and the cumulative percentage of patients achieving that change score or better will be displayed on the y-axis. The eCDF may be interpreted by choosing a change score magnitude that may be considered clinically meaningful on the x-axis and comparing the rate of subjects who achieved at least that amount of change (on the y-axis) between the treatment arms.

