#### **HRQoL Analysis Set**

The Health-Related Quality of Life (HRQoL) analysis set is a subset of the FAS and includes all FAS subjects who meet both of the following criteria:

- Maintenance Phase baseline HRQoL assessment completed
- At least one HRQoL assessment completed after start of Maintenance Phase study treatment (or after Maintenance Phase Week 1 Day 1 visit for subjects who did not receive active study treatment).

Re-baseline HRQoL assessment occurs following completion of Induction Phase chemotherapy treatment at the Re-baseline visit.

Maintenance phase HRQoL assessment is defined as HRQoL questionnaires completed after the first dose of Maintenance Phase study treatment for subjects who received avelumab or continuation of Induction phase chemotherapy treatment, and questionnaires completed after date of randomization for subjects on BSC only.

[figure not shown]

Table 1 summarizes how each of the analysis sets will be used.

**Table 1** Statistical Analyses by Analysis Set

Analysis	Analysis Set						CCI
	FAS	PD-L1+	PP	Safety-Induction	Safety-Maintenance	HRQoL	
Demographic Characteristics	✓	✓		✓	✓	✓	
Other Baseline Characteristics (Medical History, Disease History, Prior Anti-Cancer Therapies, Re-baseline RECIST response)	✓	✓		✓	✓	✓	
Prior and Concomitant Therapies/Procedures	✓	✓		✓	✓		
Compliance and Exposure				✓	✓		
Efficacy: Primary Endpoint (OS)	✓	✓	✓				
Efficacy: Key Secondary Endpoints: (PFS, BOR)	✓	✓	✓			✓ (BOR only)	
Efficacy: Other Secondary Endpoint: HRQoL		✓				✓	
CCI							
Safety Endpoints (See Section 16 for additional details)				✓	✓		
PK							✓

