### 15.2.3.3 European Organization for Research and Treatment of Cancer (EORTC) Gastric Cancer Module QLQ-STO22

The QLQ-STO22 self-assessment questionnaire is a gastric cancer module consisting of 22 items concerning disease and treatment-related symptoms and side effects, dysphagia, nutritional aspects and items about the emotional problems of gastric cancer. The module is composed of 5 multi-item symptom scales (Dysphagia, Pain, Reflux, Eating Restrictions, and Anxiety) and four single items (Dry Mouth, Tasting, Body Image, and Hair Loss) as shown in Table 7. A higher score represents more problems/ worse symptom severity.

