#### Remarks

- Item 52 is an optional item and depends on the answer to item 51. Item 52 should only be answered and assessed if 'yes' has been answered to item 51.

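### Read literally, a correctly skipped QLQ-STO22 item makes the form incomplete, and HRQoL compliance and completion are measured only in subjects selected for having returned forms

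*SAP*

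**What the plan says.** SAP 15.2.3 defines two percentages for each scheduled visit.

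- **Compliance.** The numerator is the "number of subjects with at least one HRQoL questionnaire available", taken across the three instruments. The denominator is the subjects for whom a questionnaire is expected.
- **Full completion.** The numerator is the "number of subjects with all items in HRQoL questionnaire available". The denominator is the "number of subjects for whom HRQoL questionnaire is expected".

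Both are to be plotted over time for each questionnaire, with one line per arm. Neither 'available' nor 'expected' is defined.

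On population, the section lists only the HRQoL set and states: "The analyses specified in this section will be performed for HRQoL analysis set". SAP section 9 admits a subject to that set on two conditions: "Maintenance Phase baseline HRQoL assessment completed", and "At least one HRQoL assessment completed after start of Maintenance Phase study treatment" (with a Week 1 Day 1 equivalent for subjects without active treatment). SAP Table 1 ticks the HRQoL and PD-L1+ sets for this endpoint, but not the FAS.

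SAP 15.2.3.3 describes the QLQ-STO22 as a "self-assessment questionnaire is a gastric cancer module consisting of 22 items". Appendix III calls item 52, the second hair-loss item, optional, lists hair loss as '2/1' items, and adds: "Item 52 should only be answered and assessed if 'yes' has been answered to item 51".

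**The concern.** The trial is open-label, HRQoL is a secondary objective, the arms are compared by a repeated-measures model, and missing HRQoL scores are not imputed. The compliance and completion plots are the main planned display from which a reader can judge whether missing questionnaires might bias that comparison. Two features of the definitions work against this use.

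First, the completion rule and the skip rule conflict. The better a subject without hair loss follows the instructions, the more surely the form is classed as incomplete. Hair loss may differ between avelumab and chemotherapy, so a toxicity difference could be drawn as a difference in data quality.

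Second, the rates meant to show non-response are calculated after removing subjects who never returned a baseline form, or never returned a later one.

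**Working it through.** The documents give no compliance or completion figure, so there is none to reproduce. The shares used below are assumptions; only the formulas and the item counts come from the SAP.

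**1. Full completion of the QLQ-STO22**

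Items run from 31 to 52 (SAP Table 7), so 52 − 31 + 1 = 22 items. A subject who answers 'no' to item 51, correctly skips item 52 and answers everything else has 21/22 = 95.5% of items, and fails an all-items rule.

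Let h be the share answering 'yes' to item 51, and c the share answering every applicable item (taken as independent of h). Then:

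literal full completion = h × c; intended full completion = c.

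| h | c = 100% | c = 90% |
|---|---|---|
| 10% | 10% | 9% |
| 20% | 20% | 18% |
| 40% | 40% | 36% |
| 80% | 80% | 72% |

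With h = 10% on avelumab and 30% on control, perfectly completed forms would plot as 10% and 30% instead of 100% and 100%.

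Hair-loss scoring is not affected. SAP 15.2.3 computes a scale when at least half its items are present, and one of two items meets that.

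**2. Compliance in the HRQoL set**

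Let T be true compliance among all randomized subjects for whom a form is expected at a visit, q the share of them outside the HRQoL set, and r the share of those outsiders who did return a form at that visit. Then:

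shown compliance = (T − q × r) / (1 − q).

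With T = 70%:

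| q | r = 0 | r = 35% | r = 70% |
|---|---|---|---|
| 5% | 0.70/0.95 = 73.7% | 0.6825/0.95 = 71.8% | 70% |
| 10% | 0.70/0.90 = 77.8% | 0.665/0.90 = 73.9% | 70% |
| 20% | 0.70/0.80 = 87.5% | 0.63/0.80 = 78.8% | 70% |

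The inflation reaches T/(1 − q) only when r = 0. That holds at every later visit for subjects excluded because they returned no later form. It need not hold for subjects excluded only for a missing baseline, who may have returned later forms. The bias is upward whenever excluded subjects return fewer forms than those kept, which is what selecting on return would be expected to produce.

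At baseline, in-set compliance is close to 100% by selection. If 10% of the 499 randomized subjects had no baseline form, the FAS figure would be 449/499 = 90.0%.

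**3. Effect on the arm comparison**

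Suppose 90% is shown in both arms, with r = 0 and q = 10% in one arm and 20% in the other. True compliance is 0.90 × 0.90 = 81% and 0.90 × 0.80 = 72%. The plot shows no gap where there is one of 9 points.

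**The case against.** **Non-response is reported elsewhere.** A reader might infer that an arm difference in exclusion vanishes from the report. It does not. SAP 11.1 tabulates, by randomized arm and for all randomized subjects, the number and percentage in each analysis set, including HRQoL. Demographics and disease characteristics are produced for both the FAS and the HRQoL set, so selection can be inspected. This stands. What is missing is the rate by visit, which that table cannot supply, and any trace of the excluded subjects in the plot itself.

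**The inflation formula is a ceiling.** A reader might take T/(1 − q) as the bias. It is the worst case, and part 2 of the working shows the bias falling to zero as excluded subjects approach the overall return rate. Subjects who die or leave early may also not be expected at later visits, so q at a visit need not equal the overall share outside the set.

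**Baseline compliance is not exactly 100%.** SAP section 10 accepts as baseline any form within 28 days before or on the date of randomization or, failing that, one after randomization and before the first dose. Set membership therefore does not guarantee a form at the Re-baseline visit itself.

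**'All items' could mean all applicable items.** Read with Appendix III, it could, and a programmer might do the sensible thing. But 15.2.3 does not say so, and the general rule in SAP section 10 is that data are evaluated as reported unless otherwise specified. The definition needs the exception in writing.

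**The population is not fully settled.** Text after the population sentence is blacked out, Table 1 also ticks PD-L1+, and SAP section 7 allows for a supplemental HRQoL plan. A further run in another set cannot be excluded. The visible text still names the HRQoL set and leaves the FAS unticked.

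**Conclusion.** Both parts hold as limited here. As written, the QLQ-STO22 full completion rate cannot exceed the share of subjects reporting hair loss, so an arm difference in hair loss would be displayed as a completion difference. This affects one rate for one instrument, plus any all-instrument version of it. It does not support a claim that the HRQoL scores, the compliance rate, or the EQ-5D-5L and QLQ-C30 completion rates are distorted by item 52.

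Compliance and completion in the HRQoL set are valid descriptions of that set, but compliance is biased upward as a measure for randomized subjects. For a true 70% the shown value is at most 74% to 88% with an assumed q of 5% to 20%, and lower if excluded subjects returned some forms. The documents give neither the hair-loss shares nor the exclusion shares, so the actual size is unknown.

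The rates are descriptive. They do not affect alpha, the primary tests of OS, or the key secondary tests of PFS and BOR. The point matters for judging how far the open-label HRQoL comparison can be trusted, and it should be corrected on that ground.

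**What to change.** Make two changes in SAP 15.2.3.

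1. Define full completion as all applicable items answered, with QLQ-STO22 item 52 counted as complete when item 51 is answered 'no'.
2. Compute compliance and full completion by visit and arm on the FAS, with the denominator being all randomized subjects for whom a form is due at that visit. State what makes a form due: for example, the subject is alive and on study, and the form is scheduled for that regimen. Protocol Tables 3 to 6 place the first form after Day 1 at Week 3 or Week 4 depending on regimen.

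Keep the HRQoL set for the score analyses.

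The cost is two sentences and the reprogramming of one table and plot from data already collected. The only drawback is a less favourable compliance figure.

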4.2 Secondary Objectives

Secondary objectives are as follows:

- To demonstrate superiority of maintenance therapy with avelumab versus continuation of first-line chemotherapy with regard to PFS as per RECIST v1.1 according to Investigator assessment.
- To demonstrate superiority of maintenance therapy with avelumab versus continuation of first-line chemotherapy with regard to the ORR as per RECIST v1.1 and per Investigator assessment
- To compare the subject-reported outcomes / quality of life (QoL) of subjects when treated with avelumab versus continuation of first-line chemotherapy as assessed by the European QoL 5-dimensions 5 Level Questionnaire (EQ-5D-5L), and the European Organization for Research and Treatment of Cancer (EORTC) QLQ-C30 and module QLQ-STO22
- To determine the safety and tolerability of avelumab.

5 Investigational Plan

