8.5.3.3.2 European Organization for Research and Treatment of Cancer QLQ-C30

[figure not shown]
Observed and change from baseline values for the Global health status / QoL scale and each of the five QLQ-C30 functional scales (ie, Physical, Role, Emotional, Cognitive, and Social) will be summarized descriptively at planned visits during the Maintenance Phase, the Discontinuation Visit, and End-of-Treatment Visit by treatment arm. In addition, the best (largest positive change), worst (largest negative change), and last-observed on-treatment change from baseline values will be summarized. Each measure will be compared between the two treatment arms using a mixed-effects model repeated measures (MMRM) analysis to evaluate longitudinal change from baseline using region and baseline value as covariates. This analysis will be based on the HRQoL Analysis Set.

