## 8 Changes to the Planned Analyses in the Clinical Trial Protocol

The statistical methods specified in this SAP are in accordance with protocol version 7.0 (dated 17 July 2019), with the following exception:

- Subjects randomized to the chemotherapy arm, who are designated to receive BSC-only, will have the date of their Week 1 Day 1 assessment considered as “treatment start date”. Consequently, this date will be used for determining baseline for Safety endpoints. This differs from the protocol, which specifies that the date of randomization will be used for both. Use of the Week 1 Day 1 assessment date more closely mirrors how subjects randomized to active treatment are handled.

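### SAP 15.2.3 limits the QLQ-C30 mixed model to physical function, so five of the six between-arm model comparisons planned in the protocol become descriptive, and SAP Section 8 does not declare it

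*SAP*

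**What the plan says.** Protocol 4.2 sets a secondary objective: "To compare the subject-reported outcomes / quality of life (QoL) of subjects when treated with avelumab versus continuation of first-line chemotherapy", assessed by EQ-5D-5L, QLQ-C30 and QLQ-STO22.

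Protocol 8.5.3.3.2 gives the QLQ-C30 measures to be analysed as the "Global health status / QoL scale and each of the five QLQ-C30 functional scales (ie, Physical, Role, Emotional, Cognitive, and Social"). It continues: "Each measure will be compared between the two treatment arms using a mixed-effects model repeated measures (MMRM) analysis to evaluate longitudinal change from baseline", with region and baseline value as covariates. Protocol 8.5.3.3.3 gives the same treatment to five QLQ-STO22 symptom scales.

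SAP 15.2.3 names a shorter list. Its MMRM "will evaluate longitudinal change from baseline on the QLQ-C30 physical function scale and the QLQ-STO22 symptom scales". The between-arm test belongs to that model: "The overall significance of the difference between the MMRM trajectories for the treatment arms will be tested". The subject-level display is restricted in the same way: "For the HRQoL domain scores analyzed using MMRM, an empirical cumulative distribution function (eCDF) curves, separated by treatment arm".

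SAP Section 8, where departures from the protocol are listed, says: "The statistical methods specified in this SAP are in accordance with protocol version 7.0 (dated 17 July 2019), with the following exception". The single exception that follows concerns the treatment start date, and hence the safety baseline, of control-arm subjects on best supportive care only.

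**The concern.** The protocol and the SAP give different lists of QLQ-C30 scales for the same analysis, and the SAP says that no such difference exists. An analyst who follows the SAP will not produce five comparisons that the protocol specifies under a stated secondary objective.

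The most visible omission is global health status/QoL. For the EQ-5D-5L, protocol 8.5.3.3.1 plans descriptive summaries of the index and only a data listing of the visual analogue scale. Global health status was therefore the only overall quality-of-life score with a planned between-arm model. Under the SAP no overall score has one. The trial is open-label and these outcomes are self-reported, so a reader comparing the two documents will want to know why one scale of six was kept, and neither document says. If the missing models are run later, SAP Section 4 would have them labelled in the study report as analyses that the SAP did not identify.

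**Working it through.** The plan gives no sample-size, power or alpha figure for this point. The check is a comparison of the two lists and a count.

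**Scales assigned to the between-arm MMRM**

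| QLQ-C30 scale | Protocol 8.5.3.3.2 | SAP 15.2.3 |
|---|---|---|
| Global health status/QoL | yes | no |
| Physical | yes | yes |
| Role | yes | no |
| Emotional | yes | no |
| Cognitive | yes | no |
| Social | yes | no |
| **Total** | **6** | **1** |

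Dropped from the model: 6 − 1 = 5 of 6.

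**Across both EORTC instruments.** Protocol 8.5.3.3.3 adds five QLQ-STO22 symptom scales (dysphagia, pain, reflux, eating, anxiety), which gives 6 + 5 = 11 planned MMRM comparisons. The SAP keeps the STO22 symptom scales, so on the protocol's list it models 1 + 5 = 6. The shortfall is 11 − 6 = 5 of 11.

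**Is it the same model?** Yes, in its covariates. The protocol adjusts for region and baseline value. The SAP adjusts for the Maintenance Phase baseline score and the randomization stratification factor, which is region. The SAP has not replaced the protocol's analysis of the five scales with a different between-arm model.

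**What remains for the five scales.** SAP 15.2.3 introduces its analyses as applying to each questionnaire's scores. It keeps observed values and changes by arm and visit, the percentages at the best and worst possible score, the best, worst and last change, and mean-change plots with a line per arm and 95% confidence intervals. The MMRM item then names its own scales, and the curve item confirms that only a subset is modelled. The general introduction therefore does not bring the other five scales back into the model.

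**Is it declared elsewhere?** In SAP 4.1, the visible entries for the quality-of-life section record the addition of the MMRM (version 2.0) and a clarification of baseline (version 3.0). Neither mentions a restriction of scales. Some entries in that log are redacted, but the MMRM sentence in 15.2.3 is complete.

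**Effect on error control.** Protocol 8.5.1 and SAP Section 15 make no multiplicity adjustment for non-key secondary endpoints. Restoring the five models changes no boundary, alpha level, power figure or sample size.

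**The case against.** The strongest reply is that the SAP is entitled to do this. Protocol 7.7.1 leaves the questionnaire analysis to the SAP. Protocol 8.5.1 lets the SAP modify the plan and requires an amendment only for major modifications. Narrowing a non-key, unadjusted endpoint may well not be major. This stands as far as it goes: the restriction could be legitimate. It does not rescue the statement in SAP Section 8, which lists departures and omits this one.

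Second, the protocol itself accepts descriptive reporting for the EQ-5D-5L under the same objective, so descriptive results are not an improper level of analysis. That is fair. But the protocol made a different choice for these six QLQ-C30 scales and stated it explicitly.

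Third, SAP Section 7 says that a separate or supplemental plan might cover quality of life. Such a plan is optional, and it does not secure a comparison that the protocol specifies.

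Two stronger readings are tempting. A reader might infer that the five scales get no between-arm information at all. The documents do not support that, because by-arm summaries and plots with confidence intervals remain. A reader might also infer selective reporting. The documents do not support that either: the restriction is written into the SAP, SAP 7.3 bars any database lock before the SAP is approved, and nothing suggests that the scales were chosen on results. The defect is an undeclared narrowing of the planned analysis.

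**Conclusion.** The inconsistency is real, and the SAP is wrong as written on two counts. It omits the model-based comparison for five of the six QLQ-C30 scales that the protocol assigns to it, and Section 8 claims an accordance with protocol version 7.0 that does not hold here. What is lost is the baseline- and region-adjusted longitudinal comparison, its test, and the cumulative distribution curves. Descriptive results by arm are kept. The effect is confined to a non-key secondary endpoint, and no confirmatory conclusion depends on it.

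This rests on reading the SAP's list of scales as exhaustive, which its wording and the matching restriction on the curves support. It also assumes that no separate quality-of-life plan restores the five models. The documents show no such plan, but they leave room for one.

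**What to change.** In SAP 15.2.3, extend the MMRM to global health status/QoL and all five QLQ-C30 functional scales, as protocol 8.5.3.3.2 specifies. The cumulative distribution curves then follow under the SAP's own rule. If any scale is left out on purpose, list it in SAP Section 8 with the reason, and amend the protocol if the change is judged major under protocol 8.5.1. If a separate quality-of-life plan is meant to carry these comparisons, SAP 15.2.3 should say so and refer to it.

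The cost is five more runs of a model already specified, plus their curves. All six scales are already collected, and SAP 15.2.3.2 already defines their scoring, so no new data are needed. Declaring the omission instead costs only a text change.
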